### 1) Abstract of the study

**Introduction:** Older adults have been described as one of the most underserved and vulnerable groups, who are at the highest risk for coronal and root caries, especially because more elderly adults are retaining their teeth. The Northeast Philadelphia KleinLife site is an important destination for the region's Jewish population comprising of at least 6500 seniors, and assisting more than 4500 seniors through food security programs. Recently, Temple University Kornberg School of Dentistry (TUKSoD) purchased the dental center at the facility to expand the services provided to these underserved population and improve their oral health. The study aims to assess the efficacy of an oral health education group based activity versus an individual based oral health education activity in terms of changes in oral health related quality of life (OHRQoL), self-efficacy and oral health knowledge. **Methods:** A sample of 190 senior members will be invited to participate in the trial. Potential subjects will be obtained in person through the ongoing flow of patients at TUKSoD Clinic at Kleinlife and the dental school. Seniors who consent to participate in the study will be randomly allocated to one of the 3 groups (Control: subjects will continue receiving regular dental care at the clinic, Intervention 1: subjects will continue receiving regular dental care at the clinic and be invited to participate in 2 group based education sessions during a 12 month period, and Intervention 2: subjects will continue receiving regular dental care at the clinic and be invited to participate in an individual-based education and prevention activity over a 18 month period. Randomization will be determined according to a predetermined random sequence, and neither the patient nor the research staff will be aware of the randomization outcome until after the patient has agreed to participate. Subjects who consent to participate will be entered into a raffle to receive a \$350-dollar visa gift card, if they complete the baseline and follow up assessments. The OHIP-14 will be used to assess OHRQoL, and self-efficacy scores will be the primary outcomes. Initially, we will assess the differences between the interventions and control using 2-sample *t*-tests. The main analysis will be based on linear mixed-effects models for repeated measures (using the OHIP 14 and self-efficacy scores as continuous outcome variables) to assess differences between intervention and control groups. Similar analyses will be conducted for secondary outcome measures. Statistical significance will be set at  $p < .05$ .

### 2) Protocol Title

Oral Health Education Interventions and Its Association with Behavioral Outcomes:  
A Clinical Trial

### **4) Objectives**

- **Primary Objective:**

The objective of this study is to test the efficacy of an oral health education group based activity versus an individual oral health education activity in terms of changes in oral health related quality of life (OHRQoL), self-efficacy and oral health knowledge.

- **Secondary Objective**

The secondary objective of this study is:

a) To assess differences among intervention and control groups by senior's oral health knowledge.

- **Overall Hypotheses**

Ho: There are no significant differences in the selected behavioral outcome measures between the interventions, either group-based or individual based education and the control.

Ho: The two educational interventions are not equivalent in the selected behavioral outcome measures.

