## ORAL HEALTH EDUCATION SENIORS

The objective of this study is to test the efficacy of an oral health education group based activity versus an individual based oral health education activity in terms of changes in oral health related quality of life (OHRQoL), and self-efficacy among seniors at Kleinlife and at the Dental School.

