### **c) Study Timelines**

**Table 1: Research Timelines**

Approximate Months/ Year	Goals
March 2017	IRB submission
Summer-Fall 2017	Recruitment, implementation of educational interventions and baseline data collection
Spring Summer 2018	Follow up data collection
Fall 2018	Finalize manuscript for publication

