### **Control Group: (60 seniors).**

Seniors who are randomly assigned to the control group will continue receiving regular dental care under the standard clinic operation. Subjects in this group will complete intake forms to assess main behavioral outcomes, at baseline and after 12 months. No other activities will be conducted in this group.

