### **Data Analysis:**

Initial analyses will be conducted to determine normality of distributions of the continuous variables, and any necessary transformations will be conducted. Primary outcomes will be the OHIP 14 and the self-efficacy scores. All eligible patients will be randomly assigned to 1 of the 3 groups described above. Although randomization should provide relatively comparable groups, demographic variables that differ between groups and are correlated with the primary outcomes will be used as covariates. Preliminary analysis will include measures of central tendency and dispersion, as well as an examination of the bivariate relationships among the primary and secondary outcome variables, potential moderators, and demographic characteristics.

Differences between the groups on baseline demographic, and psychological measures will be examined using  $\chi^2$  (Pearson) or Student's *t*-tests, as appropriate. Moreover, differences on the variables listed above among completers and drop-outs will also be explored. Intention to treat (ITT) analyses will then be conducted.

OHIP 14 and self-efficacy scores will be the primary outcomes. Initially, we will assess the differences between the interventions and control using 2-sample *t*-tests. The main analysis will be based on linear mixed-effects models for repeated measures (using the OHIP 14 and self-efficacy scores as continuous outcome variables) to assess differences between intervention and control groups. Similar analyses will be conducted for secondary outcome measures. Statistical significance will be set at  $p < .05$ .

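### Group versus individual education is the primary objective, but the analysis names no such contrast, and the non-equivalence null has no margin or rule that could reject it

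*Combined protocol and SAP*

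**What the plan says.** The primary objective in section 4 is to "test the efficacy of an oral health education group based activity versus an individual oral health education activity". The Abstract, section 5 (Rationale and Significance) and the Study Procedure text in section 7d repeat the comparison: "group based activity versus an individual based oral health education activity".

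Overall Hypotheses gives two nulls. The first is that neither intervention differs from control. The second is "The two educational interventions are not equivalent in the selected behavioral outcome measures".

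The Abstract and Data Analysis describe two steps for the outcomes. The first reads "Initially, we will assess the differences between the interventions and control using 2-sample" t-tests. The second, called the main analysis, is a linear mixed-effects model for repeated measures on OHIP-14 and self-efficacy, used "to assess differences between intervention and control groups". Significance is set at p < .05. No margin, TOST procedure or confidence-interval rule appears anywhere.

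The assessment times differ by arm:

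- **Control:** "at baseline and after 12 months".
- **Intervention Group 1 (group education):** baseline, 6 and 12 months.
- **Intervention Group 2 (individual education):** baseline, each follow-up visit (undated) and 18 months. The same paragraph describes the education activity as running over 12 months and the three visits as spread over 18 months; the Abstract gives 18 months for the activity.
- **Table 1 (approximate):** recruitment and baseline in summer and fall 2017, and one follow-up window, "Spring Summer 2018".

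**The concern.** The question placed first in the objectives has no matching comparison in the analysis. Followed as written, the plan reports each intervention against control and does not report group against individual. The contrast, its time point and the way it is judged could then be settled after the data are seen.

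The second null adds a separate problem. When non-equivalence is the null, rejecting it means demonstrating equivalence. A difference test at p < .05 cannot do that: a significant result does not show equivalence, and a non-significant one only fails to show a difference. Without a stated rule, a non-significant group-versus-individual result is open to being reported as equivalence.

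**Working it through.** **Step 1. Match each stated question to a stated analysis.**

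| Question (section 4) | Comparison in Data Analysis | Rule |
|---|---|---|
| Either intervention vs control (first null) | t-tests; mixed model | p < .05 |
| Group vs individual (primary objective) | none named | none tied to it |
| Not equivalent (second null) | none named | no margin, TOST or CI rule |

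**Step 2. Look for a common time.** Group education is assessed at 6 and 12 months. Individual education has one dated post-baseline assessment, at 18 months, plus undated visits. One of those visits might fall at 6 or 12 months, but no text says so. No post-baseline time is therefore stated for both intervention arms. Table 1 does not supply one: its single approximate follow-up window, in the year after baseline, fits an 18-month assessment poorly.

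**Step 3. The plan's own figure.** The arms are 60 + 60 + 70 = 190. The Intervention Group 2 and Calibration paragraphs put 10 of the 70 outside the study, leaving 180, or 60 per arm. The documents give no effect size, SD, power, dropout rate or margin, so no power calculation can be reproduced.

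**Step 4. Illustrate the precision of the missing contrast.** Work in SD units, with n per arm and baseline correlation r. Here r (0 to 0.7) and dropout (0 to 20%, so n = 60 to 48) are assumptions.

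- SE = sqrt(2(1 − r²)/n)
- 95% CI half-width = 1.960 × SE
- TOST power with identical arms = 2Φ(margin/SE − 1.645) − 1. Setting this to 0.80 gives margin = (1.645 + 1.282) × SE.

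For n = 60 and r = 0: SE = sqrt(2/60) = 0.183; half-width = 1.960 × 0.1826 = 0.358; margin = 2.926 × 0.1826 = 0.534.

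| n per arm | r | SE | 95% half-width | Margin for 80% TOST power |
|---|---|---|---|---|
| 60 | 0 | 0.183 | 0.358 | 0.534 |
| 48 | 0 | 0.204 | 0.400 | 0.597 |
| 60 | 0.7 | 0.130 | 0.256 | 0.382 |
| 48 | 0.7 | 0.146 | 0.286 | 0.427 |

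At n = 60 and r = 0, the 90% CI half-width is 1.645 × 0.1826 = 0.300 SD, so a margin of 0.3 SD or less gives essentially no power. A margin of 0.5 SD gives 73%.

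**The case against.** Five points can be made for the plan.

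- **The model already contains the contrast.** A three-arm mixed model estimates group versus individual, and with two intervention arms there is only one such pair. This stands. A reader might infer that the trial cannot answer its primary question; the documents do not support that. The contrast is available but unnamed, and no new data collection is needed apart from settling the timing.
- **A decision rule exists.** The p < .05 criterion is not limited to particular contrasts, and the second null may simply be a difference null worded in reverse. If so, the rule is usable and only the contrast and its time are missing. It would be too strong to say that the plan has no rule, or that equivalence was certainly intended. But the null as written is one of non-equivalence, and nothing in the text says otherwise.
- **The secondary objective covers it.** Its wording, "To assess differences among intervention and control groups", could loosely include the pair, but it concerns oral health knowledge and not OHIP-14 or self-efficacy.
- **The timing conflict is soft.** Table 1 is headed as approximate and gives no dates, so it does not prove that an 18-month assessment is impossible. The firmer evidence is the Intervention Group 2 paragraph, which uses both 12 and 18 months.
- **The misreading is hypothetical.** A reader might infer that the sponsor will take non-significance as equivalence. No sentence says so; the plan merely fails to rule it out.

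The figures in SD units also omit baseline adjustment in the leading case, while the planned model is a repeated-measures one. That is why the range over r is shown. The defect does not depend on those figures.

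**Conclusion.** The point holds and should be fixed before analysis. The text alone shows that the primary comparison has no named contrast or time point, and that the second null as written cannot be rejected by anything in the plan. The p < .05 criterion serves only if that null is a difference null in reverse.

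The size is illustrative. With 60 per arm, no dropout and no baseline adjustment, the contrast would be estimated to about ±0.36 SD, and an equivalence claim with 80% power would need a margin of about 0.53 SD. Under the assumed dropout and correlation ranges, these run from 0.26 to 0.40 SD and from 0.38 to 0.60 SD. Whether margins of that size are acceptable for OHIP-14 or self-efficacy cannot be judged from the documents.

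**What to change.** 1. **State which aim was meant.**
   - *Difference:* reword the second null to say that there is no difference between group-based and individual-based education. Test it at the stated p < .05, report the confidence interval, and state that non-significance will not be read as equivalence.
   - *Equivalence:* keep the null, and state in advance a justified margin for each primary outcome with a 90% CI/TOST rule.
2. **Name the contrast.** In Data Analysis, specify group versus individual from the planned mixed model as a primary contrast for OHIP-14 and self-efficacy, which the Abstract and Data Analysis already name as primary. Take it at one assessment time common to both intervention arms.
3. **Reconcile the schedule first.** Table 1, the three arm descriptions and the Abstract must agree, so that such a time exists. Which time that is remains for the sponsor to decide.

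The cost is rewording in Objectives and Data Analysis, one extra contrast per primary outcome from a model already planned, and the reconciliation of the schedule. The equivalence claim is given up unless a margin can be justified. Without baseline adjustment, a margin much below about 0.5 SD would be underpowered at 60 per arm.

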### **5) Rationale and Significance**

Older adults or the elderly have been described as one of the most underserved and vulnerable groups. Many studies have shown that elderly adult population groups are at a higher risk for coronal and root caries, especially because more elderly adults are retaining their teeth. KleinLife is an important destination for the region's Jewish population. KleinLife comprises of at least 6500 seniors, and has assisted more than 4500 seniors through food security programs. The Northeast Philadelphia KleinLife site also has a dental center that provides routine care to the members who seek care. The Temple University Kornberg School of Dentistry (TUKSoD) recently purchased this dental center to expand the services provided to these underserved population and improve their oral health.

## ORAL HEALTH EDUCATION SENIORS

KleinLife is a vibrant community resource that provides social, educational and cultural programs, and vital health, wellness and social services to the multigenerational, ethnically diverse membership it serves. Individuals regularly come together to participate in enrichment offerings, receive vital services, enjoy each other's company, and connect to additional resources and support. KleinLife is an important destination for the region's Jewish population, both young and old. It serves as a lively home-away-from-home for seniors and a welcoming gathering place for Russian Jews. More than 7800 health care referrals to seniors and their families have been made through KleinLife.

TUKSoD and KleinLife's staff conducted a survey in December 2015 to develop a baseline needs assessment that would inform the development and implementation of a tailored oral health care model in this community. Two hundred oral health surveys were completed and from this initial survey, we learned that there were variations in knowledge, attitudes and practices related to oral hygiene among seniors and lack of understanding of key fundamental concepts in oral health education and oral health related quality of life.

Recent studies on this area have mainly focused on the effects of oral health educational interventions for caregivers at improving dental health among seniors but very few interventions report on the oral health-related knowledge and other important behavioral outcomes of seniors themselves. MacEntee et al in 2007 reported no significant changes to oral health of seniors with a pyramid-based educational intervention, however, in 2012, De Visschere et al reported a small, but statistically significant improvement in denture plaque following a 6-month supervised educational intervention.

A recent systematic review (Kay et al, 2016) showed that the motivational interviewing technique, which is based on the concept of autonomy support, has potential for helping patients with poor oral health. However, most of the studies appraised involved children and young adults or seniors with periodontal conditions and the outcomes examined were exclusively clinical. Relying on clinical indicators becomes problematic when evaluating the efficacy of educational interventions among adults as often times these populations are edentulous or partially dentulous and do not reveal the impact on additional behavioral and cognitive outcomes which in turn may affect the overall well-being of the individual. Moreover, although low parental self-efficacy has been associated with adverse dental outcomes among children, there has been little documented evidence of the role of self-efficacy in adult oral health outcomes. Even less has been reported on groups known to be at high risk of dental disease such as the elderly. There is a lack of information on how different types of oral health education activities may affect seniors oral health related quality of life and self-efficacy. These studies present a case for additional research on senior's self-efficacy, and oral health care knowledge, along with training interventions aimed at improving the poor oral health of the elderly.

## ORAL HEALTH EDUCATION SENIORS

The objective of this study is to test the efficacy of an oral health education group based activity versus an individual based oral health education activity in terms of changes in oral health related quality of life (OHRQoL), and self-efficacy among seniors at Kleinlife and at the Dental School.

### **6) Resources and Setting**

All patients will be identified and evaluated at the dental clinic of the Temple University Kornberg School of Dentistry (TUKSoD) located in Kleinlife and at the Dental School. All participants will be provided with consent forms. All research staff has CITI training and will be required to read all the documentation related to the study and discuss any questions with the investigators before initiation of activities.

### **6) Prior Approvals**

Not Applicable

### **7) Study Design**

#### **a) Recruitment Methods**

Approximately 190 subjects, older than 55 years old will be recruited for the purpose of the study. There are no restrictions in terms of relative numbers of females and males. Potential subjects will be obtained in person through the ongoing flow of patients at TUKSoD Clinic at Kleinlife and at the Dental School. The research staff will also be available during regular operating hours to inform and recruit patients at the lobby at Kleinlife and at the Dental School. The consent form (See Appendix A) to participate in the study will be provided to the senior and if they decide to participate they will be entered into a raffle to receive a \$350-dollar visa gift card, if they complete the baseline and follow up assessments. The information from the consent forms will only be used for the purpose of the raffle. This is required for compliance with Pennsylvania state laws. Information about the study will also be posted in a flyer (See Appendix B) in designated areas at Kleinlife and at the Dental School.

#### **b) Inclusion and Exclusion Criteria**

There are no restrictions on enrollment in terms of gender, economic status, race or ethnic group.

#### **Inclusion criteria**

##### **Patients:**

- 1) Must be 55 years old or older.
- 2) May be new, regular, emergency patients attending the TUKSoD clinic at Kleinlife or clinics at the Dental School or utilizing medical and social services at Kleinlife who have the intention to become patients of record at the dental clinic.

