### **Exclusion criteria:**

#### **Patients:**

- 1) Subjects younger than 55 years old will be excluded from the study.
- 2) Subjects who do not provide consent for participation will be excluded from the study.
- 3) Subjects who do not speak and understand English.

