## ORAL HEALTH EDUCATION SENIORS

study:

- Oral Health Related Quality of Life: The Short-Form Oral Health Impact Profile (OHIP-14; Slade, 1997) is a 14-item self-report measure that assesses individuals' perceptions of the social impact of oral conditions on their well-being. This scale evaluates the consequences of oral conditions across dimensions of functional limitation, physical pain, psychological discomfort, physical disability, psychological disability, social disability, and handicap. Items are rated on a 5-point Likert-type scale ranging from 0 (*never*) to 4 (*very often*), regarding how frequently impact has been experienced. The total score ranges from 0 to 56; higher OHIP-14 scores indicate greater impact, hence poorer oral-health-related quality of life. The OHIP-14 has been validated in two national surveys of populations in the UK and Australia (Kelly et al., 1998; Steele et al., 2004) and demonstrated good reliability, construct and discriminant validity, and internal consistency (Slade & Spencer, 1994; Slade, 1997).
- Self-efficacy will be assessed based on a modified version of an instrument developed by Finlayson and colleagues (Finlayson et al, 2007). It will be measured using a 6-item scale, asking participants to indicate how confident they feel about their ability to brush their teeth at night when they were: (1) under a lot of stress; (2) depressed; (3) anxious; (4) feeling that they were too busy; (5) tired or; (6) worried about other things in their life. The four response options range from 'very confident' to 'not at all confident'. The possible score range is 0 to 24, with high scores indicating high self-efficacy. Alpha was 0.91. Self-efficacy will be dichotomized based on a median split, with low self-efficacy pertaining to scores of 0 to 11 and high self-efficacy pertaining to scores of 12+.
- Oral Health Knowledge: A 15-item questionnaire with a three-point Likert Scale (yes, no, and don't know) will be used to assess the oral health information/knowledge of the seniors pre and post intervention. Its respective psychometric properties (validity and reliability) have already been reported (Khanagar et al, 2014).
- Demographic Factors Questionnaire will identify key demographic factors such as age, sex, race, ethnicity, education and income level of seniors.

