### **Data Management:**

All demographic information and questionnaires will be administered in person. Data will be entered into an excel spreadsheet. Data will be downloaded to an IBM-compatible computer and stored on a password-protected account, and it will be exported to a computer data analysis program (SAS/SPSS). Data will be cleaned and checked for errors prior to the analysis; imputation procedures for handling missing data will be conducted depending on the number of cases with missing data. Participant names and corresponding identification numbers will be stored separately in a locked file cabinet or password-protected file.

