**Oral Health Self Efficacy Scale**

Seniors oral health self-efficacy measure:

*Oral Health Self-efficacy (OHSE) - Scale: 4=very confident, 1=not at all confident.*

1. under a lot of stress
2. depressed
3. anxious
4. feeling like you do not have the time (too busy)
5. tired
6. worrying about other things in your life
7. bothered by your crying child
8. bothered because your child doesn't stay still when you want him or her to brush

ORAL HEALTH EDUCATION SENIORS

9. told by your child that he/she does not feel like brushing right now

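### The self-efficacy primary outcome is about brushing one's teeth, but edentulous seniors are eligible and dentition is not recorded, so for an unknown share the score may not measure the intended construct

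*Combined protocol and SAP*

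**What the plan says.** **Eligibility.** Section 7b covers age, clinic or KleinLife attendance, English and consent. The age rule is "Must be 55 years old or older", mirrored in the exclusions by "Subjects younger than 55 years old will be excluded from the study". No criterion concerns natural teeth.

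**Expected population.** Section 5 argues against relying on clinical indicators because "often times these populations are edentulous or partially dentulous". The Abstract and Section 5 also say that more older adults now keep their teeth. No percentage is given for either statement.

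**Outcome.** Section 7d (Data Analysis) names OHIP-14 and self-efficacy as the primary outcomes. Section 7d (Measurements) describes self-efficacy as a modified six-item scale, "asking participants to indicate how confident they feel about their ability to brush their teeth at night when they were" in each of six states such as stressed or tired. The Appendix C form lists the situations and gives "Scale: 4=very confident, 1=not at all confident". It prints no question stem, no mention of dentures and no not-applicable option.

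**Dentition data.** The Appendix C demographic form asks for ZIP code, gender, age, education, income, race and ethnicity. Section 7f limits chart access to intervention group 2, for oral hygiene behaviors and systemic diseases.

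**Missing data.** Section 7d (Data Management) says "imputation procedures for handling missing data will be conducted depending on the number of cases with missing data". No rule covers items that do not apply to a participant.

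**The concern.** The plan recognises that missing teeth undermine clinical measures in this population, but it does not carry that reasoning over to a primary outcome that is about tooth brushing. A senior with no natural teeth could leave the items blank, choose the lowest confidence, or answer about cleaning a denture. The documents give no instruction, so participants may differ in what they do, and the resulting scores would not share one meaning.

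What is at stake is the between-arm difference in self-efficacy. If some participants' scores cannot move with education, the difference shrinks. Because dentition is not collected in all arms, the analyst could neither measure the problem nor run a sensitivity analysis around it.

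**Working it through.** **1. Set the instruments side by side.**
- OHIP-14 (Appendix C): 13 of the 14 items name dentures alongside teeth and mouth; the other (item 3) asks about the mouth. All 14 can be answered by someone without teeth.
- Knowledge form (Appendix C): items 2, 9 and 10 concern dentures and item 8 concerns people with no teeth.
- Self-efficacy: the description is "how confident they feel about their ability to brush their teeth at night when they were", and nothing in the form widens it. Three child-related items (7 to 9) also remain on the form, although Section 7d describes six items. The adaptation to seniors is therefore incomplete on its face.

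**2. Can edentulous participants be identified?** None of the Appendix C forms records dentition. Charts are used in one arm of three and for other content. As planned, a comparison by dentition across the arms is not possible.

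**3. Where could a blank score end up?** Six items scored 1 to 4 give a range of 6×1 = 6 to 6×4 = 24, whereas Section 7d says "The possible score range is 0 to 24, with high scores indicating high self-efficacy". A total of 0 is reachable only if blanks count as 0. The plan does not say that they do. If they did, a senior who left all six blank would fall into the low group (0 to 11).

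**4. Sample size.** 60 + 60 + 70 = 190. Ten of the 70 are calibration patients outside the trial, so 180 are in the comparison, 60 per arm. No power calculation is given, so there is no planned effect to reproduce.

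**5. Dilution.** Let *e* be the edentulous share (not in the documents; assumed 10% to 25%), and assume their scores do not respond to education. Observed difference = (1 − *e*) × true difference.
- *e* = 0.10: 6 of 60 per arm; 0.90 of the true difference.
- *e* = 0.25: 15 of 60 per arm; 0.75 of the true difference.

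Analysing dentate participants only would keep the full effect. The standard error would rise by √(60/54) = 1.05 or √(60/45) = 1.15.

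**6. Power.** Two-sided 0.05 is assumed, since sidedness is not stated. With SD 1 and 60 per arm, the difference detectable at 80% power is *d* = (1.960 + 0.842) × √(2/60) = 0.51. For two arms of size *n*, power = Φ(effect × √(*n*/2) − 1.96).
- Kept in, no response, same SD: effect = 0.51(1 − *e*), *n* = 60.
- Identified and left out: effect = 0.51, *n* = 60(1 − *e*).

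| Assumed share | Edentulous of 180 | Power, kept in | Power, left out | Gain (points) |
|---|---|---|---|---|
| 5% | 9 | 76% | 78% | 2 |
| 10% | 18 | 71% | 76% | 4 (75.7 − 71.3) |
| 20% | 36 | 61% | 71% | 10 |

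The gain from leaving them out is smaller than the dilution alone suggests, because participants are lost as well.

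**The case against.** The strongest reply is that the affected group may be small. Section 5 says edentulous *or partially dentulous*, and partially dentate seniors have teeth to brush. The plan also says that more older adults are keeping their teeth, and recruits may be as young as 55. This stands: the share is unknown, and 10% to 25% is only an assumption.

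A second reply is that the question as participants would hear it is not visible. Appendix C prints no stem, and the brushing wording comes from the description in Section 7d. Forms are given in person, so staff could clarify, and a denture wearer may answer about denture care, which the knowledge form treats as part of oral health. A reader might infer that part of the sample has no valid score at all. The documents do not establish that. They show only that the defined construct does not fit these participants and that no written instruction makes answers consistent.

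Two further inferences also go too far. One is that unequal numbers of edentulous seniors would bias the arm means. After randomisation such an imbalance is ordinary sampling error, and a score that is low but fixed at both baseline and follow-up largely cancels from change. The other is that blank scores will be imputed. Imputation is conditional in the plan and no method is named, so this is a possibility only.

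Finally, restricting the primary analysis to dentate seniors would sit uneasily with the intention-to-treat analyses in Section 7d, and the two primary outcomes would then cover different populations. That objection is sound, and the proposed change avoids it.

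**Conclusion.** The point holds as a mismatch between who may enrol and what one primary outcome is defined to measure, with no data collected in all arms to examine it. The likely harm is dilution and unclear meaning of the score.

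Its size cannot be read from the documents. A reduction to 75% to 90% of the true difference rests on two assumptions: a 10% to 25% edentulous share, and no response in that group. The second is a worst case for dilution; if denture wearers answer about denture care and respond to education, the loss is smaller. On the same worst case, identifying and excluding these participants would gain only about 2 to 10 points of power at shares of 5% to 20%.

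The modest size does not make the point one of mere wording. The plan as written gives a weaker primary outcome than a nearly free alternative, and dentition not recorded at baseline may be hard to recover later.

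**What to change.** Before enrolment:

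1. Add a baseline question to Appendix C in all three arms: any natural teeth (yes/no) and dentures worn (yes/no).
2. Print the self-efficacy stem on the form and, at every assessment, word it as *brush your teeth or clean your dentures*. Self-efficacy can then be analysed in all randomised participants, in line with the intention-to-treat plan.
3. Provide a not-applicable code, chiefly for a senior with neither teeth nor dentures. State that items so recorded are not imputed and are not scored 0.
4. Pre-specify a sensitivity analysis of self-efficacy in participants with at least one natural tooth at baseline. Dentition at baseline is not affected by allocation, so the randomised comparison is preserved within that subset.

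The cost is one more form item and a few sentences in the analysis section. The real downside is that the alpha of 0.91 quoted in Section 7d may not carry over to the reworded scale. Since the instrument is already a modified version, its reliability would best be reported from the trial's own baseline data in any case.
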